9.6.2 Duration of Response

The duration of overall response (DOR) defined as the interval from the first documentation of response to the earlier of the first documentation of definitive disease progression or death from any cause. Subjects who had the event after the start of subsequent therapy, or are progression-free and alive at the time of data cutoff, or have unknown status will be censored at the last tumor assessment on or before the start of subsequent therapy and data cut-off time. The censoring rules for DOR are summarized in [Appendix 12.2](#). The summary of DOR including mean, minimum, maximum, Q1 and Q3 are provided for all the responders for each disease group.

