#### **Duration of Response**

The duration of overall response defined as the interval from the first documentation of response to the earlier of the first documentation of definitive disease progression or death from any cause. Kaplan-Meier methods will be used to estimate event-free curves and corresponding quartiles (including the median). Data from surviving, non-progressing subjects

will be censored and detailed censoring rules will be specified in the statistical analysis plan (SAP).

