9.6.6 Analysis Methods

The analysis of DOR will be conducted on the subset of the All-treated Population who are defined as responder in protocol section 4.2. The analysis of PFS and OS will be conducted on the All-treated Population. The analysis of DOR, PFS, and OS will be estimated using the Kaplan-Meier (KM) method. KM estimates with 95% CIs will be calculated for event time quartiles, and event-free rates will be calculated at selected time points. In addition, the reason for censoring will be summarized for DOR, PFS and OS.

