12.2 Censoring Rules for Duration of Response

Situation	Outcome	Date	Event Description/ Censoring Reason
Progression documented between scheduled visits on or before receiving subsequent anticancer therapy or data cutoff, whichever occurred first	Event	Earliest date of disease assessment documenting progression	PD
Death without documented PD on or before receiving subsequent anti-cancer therapy or data cutoff, whichever occurred first	Event	Date of Death	Death
New anti-cancer treatment Started before PD or death for subjects with or without documented PD or death and before data cutoff	Censored	Date of last adequate disease assessment prior to subsequent anti-cancer treatment	New anti-cancer therapy
No documented PD or death at the time of data cutoff and subject not received subsequent anti-cancer therapy or subsequent anti-cancer therapy start date after the data cutoff	Censored	Date of last adequate disease assessment on or before data cutoff	Data cutoff
Withdrew consent before documented PD or death	Censored	Date of last adequate disease assessment	Withdrew consent
Lost to follow-up before documented PD or death	Censored	Date of last adequate disease assessment	Lost to follow-up

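### SAP 9.6.2 asks for a mean, range, Q1 and Q3 of DOR over all responders, although some durations are censored; read as ordinary statistics, the mean is biased downward and Q3 may be too

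*SAP*

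**What the plan says.** SAP 9.6.2 runs DOR from first documented response to progression or death. Responders who are event-free at cutoff, have unknown status, or have their event only after subsequent therapy "will be censored at the last tumor assessment on or before the start of subsequent therapy and data cut-off time". SAP Appendix 12.2 agrees; its data-cutoff row uses the "Date of last adequate disease assessment on or before data cutoff". Section 9.6.2 then closes with: "The summary of DOR including mean, minimum, maximum, Q1 and Q3 are provided for all the responders for each disease group". It does not restrict this to completed durations, names no estimator and does not list the median.

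SAP 9.6.6 sets the analysis set ("The analysis of DOR will be conducted on the subset of the All-treated Population who are defined as responder in protocol section 4.2") and the method: "The analysis of DOR, PFS, and OS will be estimated using the Kaplan-Meier (KM) method". It adds: "KM estimates with 95% CIs will be calculated for event time quartiles, and event-free rates will be calculated at selected time points".

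Protocol 5.5.4, under Duration of Response, says: "Kaplan-Meier methods will be used to estimate event-free curves and corresponding quartiles (including the median"). It mentions no mean or range for DOR. SAP section 10 declares no major change from the protocol's analyses.

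**The concern.** A censored duration is a lower bound on the response, not its length. An ordinary mean or quartile over all responders treats it as a completed response, so the summary is pulled down, and more so in cohorts whose responses last.

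The protocol's rationale asks whether a targeted combination can give more durable responses than single agents, whose responses in aggressive histologies can last under 12 months. A DOR summary that is too low exactly where responses are durable would blur that question and compress differences between disease groups. It could also put in the report a second set of DOR quartiles that disagrees with the Kaplan-Meier set. The median, which the protocol names, is missing from the 9.6.2 list.

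**Working it through.** The documents state no DOR median, event count or censoring fraction, so there is no figure of the plan's own to reproduce. The check has three parts.

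**1. Which reading does the text support?**
- SAP 9.6.3 (PFS) gives the same kind of list and then, on a separate line, a summary of Kaplan-Meier estimates. SAP 9.6.5 (OS) follows the same pattern.
- SAP 9.6.4 (time to next treatment) puts the same kind of list under descriptive statistics and limits it to subjects who had a next treatment. That is not Kaplan-Meier.
- A mean, minimum and maximum over all responders are not among the outputs that 9.6.6 lists.

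Ordinary descriptive statistics is therefore the natural reading, but it is an inference.

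**2. Direction of the bias.** Let T be the true duration, C the censoring time and X = min(T, C) the recorded time. X never exceeds T, so the plain mean is below the true mean whenever there is censoring. The Kaplan-Meier curve lies on or above the empirical survival curve of X, so a plain quartile cannot exceed its Kaplan-Meier counterpart. In 5,000 simulated cohorts of 4 to 24 responders (assumed median 12 months, censoring uniform over 6 to 30 months) it never did. The plain Q1 was strictly lower in 20% of cohorts and the plain Q3 in 89%, counting an unreached Kaplan-Meier quartile as higher.

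**3. Size, under stated assumptions.** Take T exponential with median m and C uniform on (a, b), independent of T. Then:
- true mean = m / ln 2
- censored fraction c = (2^(-a/m) − 2^(-b/m)) / [(ln 2 / m)(b − a)]
- plain mean = (1 − c) × true mean
- plain Q3 is the t that solves 2^(-t/m) × P(C > t) = 0.25

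Two cases worked through for m = 12 (true mean 12 / 0.6931 = 17.3):
- Censoring over 6 to 30: c = (0.7071 − 0.1768) / 1.3863 = 0.383, and the plain mean is 0.617 × 17.3 = 10.7. At t = 15.4, 0.411 × (14.6 / 24) = 0.25, so Q3 is 15.4.
- Censoring over 24 to 48: c = (0.25 − 0.0625) / 1.3863 = 0.135, and the plain mean is 0.865 × 17.3 = 15.0. At t = 24, 0.25 × 1 = 0.25, so Q3 is 24 and unaffected.

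| Assumed median DOR | Assumed censoring | Censored | Mean: plain / true | Q3: plain / true |
|---|---|---|---|---|
| 12 months | 6–30 months | 38% | 10.7 / 17.3 | 15.4 / 24 |
| 12 months | 24–48 months | 14% | 15.0 / 17.3 | 24 / 24 |
| 24 months | 6–30 months | 61% | 13.6 / 34.6 | 19.5 / 48 |
| 24 months | 24–48 months | 36% | 22.1 / 34.6 | 32.6 / 48 |
| 6 months | 24–48 months | 2% | 8.5 / 8.7 | 12 / 12 |

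In this model the proportional shortfall of the mean equals the censored fraction. In the last row that is 2.1% by formula; a simulation of 20,000 durations gave 8.4 against 8.7, about 3%. The plain Q1 is unaffected in every row except the fourth-listed median's early-censoring case (24 months, 6–30), where it is 7.6 against 10.0.

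**Which censoring range fits better?** Protocol 5.1 says enrollment closed in May 2017, and the SAP is dated 17 January 2020, so the last subject was then about 32 months past enrollment. That favours the later range. It is not decisive: the data cutoff is not given, DOR starts at response rather than at enrollment, and new therapy, withdrawal and loss to follow-up all censor earlier.

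**The case against.** The strongest reply is that 9.6.2 never says the statistics are plain. Its summary follows directly on the censoring rules, and 9.6.6, headed Analysis Methods, makes Kaplan-Meier the estimator for DOR and promises "KM estimates with 95% CIs will be calculated for event time quartiles". Q1 and Q3 in 9.6.2 could be those quartiles. The separate Kaplan-Meier line belongs to PFS and OS, not to DOR, and 9.6.5 attaches a minimum and maximum to Kaplan-Meier output, so the labels are loose throughout. This stands in part. A reader might infer that the SAP is certain to report two conflicting sets of DOR quartiles; the text makes that likely, not certain. The mean has no such rescue.

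A reader might also infer that DOR will be analysed without regard to censoring. The documents do not support that: 9.6.6 and protocol 5.5.4 both keep the Kaplan-Meier analysis. Nor is every descriptive statistic barred. Protocol 5.1 and SAP 9.1 allow descriptive summaries in general, the protocol adding that they apply as appropriate, and a plain mean of censored times is hard to call appropriate.

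Finally, a reader might take the early-censoring figures as the expected error. The enrollment and SAP dates point to later censoring, where the bias is smaller and Q3 may be unaffected.

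The stakes are also limited. The primary objective is safety, SAP section 5 tests no formal hypothesis, and the Part 2 activity criterion is ORR.

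**Conclusion.** The point holds as a defect in one summary, not in the DOR analysis as a whole. On the natural reading, the mean in 9.6.2 is biased downward whenever a responder is censored. Q1 and Q3 can fall below the Kaplan-Meier quartiles; this mainly concerns Q3, when censoring is early or heavy, while Q1 is often unchanged.

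The size cannot be fixed from the documents. Under the assumed exponential model with independent uniform censoring, the shortfall in the mean runs from about 2% (6-month median, late censoring) through 14% and 36% (12- and 24-month medians, late censoring) to 61% (24-month median, early censoring). The valid Kaplan-Meier estimate remains planned, so the harm is a misleading second summary beside it. The correction is worth making because it is cheap and restores the median that the protocol names.

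**What to change.** In SAP 9.6.2:
- Delete the mean. It cannot be recovered without further assumptions when the longest durations are censored.
- State that Q1, median and Q3 are Kaplan-Meier estimates with 95% CI, as in SAP 9.6.6 and protocol 5.5.4. This adds the missing median; Q1 and Q3 need not be dropped.
- Keep the range if wanted, with censored values marked '+'.

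The similar lists in 9.6.3 and 9.6.5 deserve the same clarification. The cost is SAP wording and table shells, with no new data and no change to design or sample size.

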9.6.3 Progression-free Survival

Progression-free survival (PFS) is defined as the interval from the first dose date of acalabrutinib or pembrolizumab to the earlier of the first documentation of objective disease progression or death from any cause. Subjects who had the event after the start of subsequent therapy, or who are progression-free and alive at the time of data cutoff, or have unknown status will be censored at the time of their last disease assessment on or before the start of subsequent therapy and data cut-off. Subjects with no post baseline disease assessment will be censored on Day 1. The censoring rules for primary and sensitivity analyses of PFS are summarized [Appendix 14.4](#).

The summary of PFS including the mean, minimum, maximum, median, Q1 and Q3 are provided for all the responders for each disease group.

Summary of K-M estimates of PFS and 95% CIs as proper for each disease group

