9.6.5 Overall Survival

The duration of OS will be measured from the time of first study drug administration until the date of death from any cause. Subjects who are known to be alive as of their last known status will be censored at their last date known to be alive. Subjects who are lost in follow-up will be censored at the date the subject is last known to have been alive. The censoring rules for OS are summarized [Appendix 14.5](#).

The summary of OS including the mean, minimum, maximum, median, Q1 and Q3 are provided for all the responders for each disease group.

Summary of 24 months K-M estimates of probability of OS including min, max, median and 95% CIs are provided for each group as well.

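### The descriptive PFS and OS lines in SAP 9.6.3 and 9.6.5 cover responders only, although both endpoints run from first dose and SAP 9.6.6 analyses them on the All-treated Population

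*SAP*

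**What the plan says.** - **Time origin.** SAP 9.6.3: "Progression-free survival (PFS) is defined as the interval from the first dose date of acalabrutinib or pembrolizumab", ending at progression or death. SAP 9.6.5: "The duration of OS will be measured from the time of first study drug administration until the date of death from any cause".
- **Who is summarised.** SAP 9.6.3: "The summary of PFS including the mean, minimum, maximum, median, Q1 and Q3 are provided for all the responders for each disease group". SAP 9.6.5: "The summary of OS including the mean, minimum, maximum, median, Q1 and Q3 are provided for all the responders for each disease group".
- **Separate Kaplan-Meier lines.** SAP 9.6.3 adds: "Summary of K-M estimates of PFS and 95% CIs as proper for each disease group". SAP 9.6.5 adds: "Summary of 24 months K-M estimates of probability of OS including min, max, median and 95% CIs are provided for each group as well". Neither mentions responders.
- **Analysis population.** SAP 9.6.6: "The analysis of PFS and OS will be conducted on the All-treated Population", by Kaplan-Meier, with confidence intervals for the quartiles. For duration of response (DOR) it says: "The analysis of DOR will be conducted on the subset of the All-treated Population who are defined as responder".
- **Protocol.** Section 5.3 places the primary efficacy analyses on the All-treated population. Section 5.5.4 asks for Kaplan-Meier curves, quartiles and median for PFS, and similar methods for OS. It sets no responder limit.
- **Declared changes.** SAP section 10 reports no major departure from the protocol's analyses.
- **Time to next treatment.** SAP 9.6.4 limits its summary to responders who went on to another treatment. SAP 9.6.6 does not mention this endpoint. Protocol 5.5.4 plans Kaplan-Meier for it, with subjects who had no further therapy censored.

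**The concern.** Response is seen only after treatment starts, and a subject must live long enough without progression to achieve it. Counting time from first dose while selecting on response does two things. It removes subjects who progressed or died early, and it credits those who remain with the event-free time they needed in order to be selected (guarantee time). Responders are the right set for DOR because that clock starts at the response. They are the wrong set for an endpoint that starts at first dose.

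PFS and OS are secondary objectives in a study without a comparator, so readers are likely to set each cohort's median against outside data. As written, two different medians for one disease group would both comply with the SAP, and one of them is biased upward.

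**Working it through.** The plan states no figure for this point, so there is none to reproduce. The check compares the texts and then illustrates the size.

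**1. Texts side by side.** SAP 9.6.3 and 9.6.5 give a median and quartiles on responders. SAP 9.6.6 gives a median and quartiles on all treated subjects. Protocol 5.3 and 5.5.4 agree with 9.6.6. The conflict is therefore inside the SAP as well as with the protocol, and SAP section 10 does not declare it.

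**2. How many subjects are left out.** Inputs: up to 30 subjects per histology (protocol 3.0, SAP 3.1) and a minimum response rate of interest of 20% (protocol 5.2, SAP 3.2). The 50% and 80% rates are added for range.

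- 20%: 30 × 0.20 = 6 summarised, 24 omitted
- 50%: 30 × 0.50 = 15 summarised, 15 omitted
- 80%: 30 × 0.80 = 24 summarised, 6 omitted

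**3. Guarantee time alone.** Assumptions: exponential PFS; response unrelated to outcome; response possible only while event-free, at Week 8 with probability q or at Week 19 with probability q/2. The scan weeks are read from a broken table in protocol Appendix 5. Week 8 is 8 × 7 / 30.4375 = 1.84 months. The 3.4-month median borrows the median exposure in protocol 1.4.2.1; the other medians are chosen for range.

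If response were possible only at Week 8, the responder median would be 1.84 months plus the true median. For 3.4 months that is 5.24, and 1 − 2^(−1.84/3.4) = 31% of subjects would have had their event by then. Allowing Week 19 as well, simulation of 400,000 subjects per case gives:

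| True (All-treated) median, months | Responder median, q = 0.2 | Responder median, q = 0.4 | Upward shift |
|---|---|---|---|
| 2.0 | 4.35 | 4.22 | 2.22 to 2.35 |
| 3.4 | 5.83 | 5.72 | 2.32 to 2.43 |
| 6.0 | 8.48 | 8.36 | 2.36 to 2.48 |
| 12.0 | 14.57 | 14.44 | 2.44 to 2.57 |

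Response rates in these cases ran from 12% to 45%.

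**4. Guarantee time plus better prognosis in responders.** Assumptions: a fraction p respond at Week 8 and then have exponential PFS with median 10 months; the rest have exponential PFS with median 2 months. After Week 8,

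S(t) = p × 2^(−(t − 1.84)/10) + (1 − p) × 2^(−t/2).

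The responder median is 1.84 + 10 = 11.84 months whatever p is. Solving S(t) = 0.5 gives:

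| Response rate p | All-treated median, months | Gap to 11.84, months |
|---|---|---|
| 25% | 2.96 | 8.9 |
| 50% | 4.8 | 7.0 |
| 80% | 8.9 | 2.9 |
| 95% | 11.1 | 0.7 |

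The gap is driven mainly by the assumed prognosis difference and by how many non-responders there are to omit.

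**The case against.** **The correct analysis is already planned.** A reader might infer that non-responders are dropped from PFS and OS altogether. The documents do not support that. SAP 9.6.6 specifies Kaplan-Meier medians and quartiles on all treated subjects, and the separate Kaplan-Meier lines in 9.6.3 and 9.6.5 carry no responder limit. The restriction sits in one descriptive line per endpoint. This part of the objection stands. What remains is that a second, differently based median is also specified. The 24-month OS line follows directly on the responder sentence and says only that it is for each group, so its population could be misread too.

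**It may be a slip.** The same phrase occurs in SAP 9.6.2, where it suits DOR, and may have been carried over. That is an inference. A table clearly labelled as responders only would describe another set and would not contradict the All-treated result. The risk is that the median is not so labelled.

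**Week 8 is not a universal gate.** A reader might infer that no subject with an event before the Week 8 scan could ever be counted. That does not hold in every disease group. Disease markers in MM and WM are scheduled at Weeks 3 and 6 (protocol Appendix 5, broken table). WM response includes minor response, which rests on IgM (SAP 9.6.1.1, protocol Table 7). The nodal criterion in CLL is under physical examination, with CT optional (protocol Table 6). Guarantee time may be shorter there, though it is not zero.

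**The size varies.** A reader might take about 3 against 12 months as the expected distortion. That is one low-response scenario. Protocol 1.4.3 reports monotherapy response rates of 80.6% in relapsed/refractory MCL and 96.9% in relapsed/refractory CLL. At rates like those, the same model gives a much smaller gap.

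**Conclusion.** The descriptive lines in SAP 9.6.3 and 9.6.5 are wrong as written and conflict with SAP 9.6.6 and protocol 5.3 and 5.5.4. The bias is upward unless response goes with a worse later outcome, which nothing in the documents suggests. Its size rests on assumed medians, response rates and response timing. It is about 2.2 to 2.6 months from guarantee time alone, and from about 9 months to under 1 month in the mixture model as the response rate rises from 25% to 95%.

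This should be fixed, but it does not undermine the trial. PFS and OS are secondary, SAP section 5 plans no formal hypothesis test, no decision rule in the documents uses these endpoints, and the valid analysis is in 9.6.6. SAP 9.6.4 is the weaker spot. Its restriction also drops everyone without a next treatment, and no section of the SAP supplies the Kaplan-Meier analysis that the protocol plans.

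**What to change.** - **SAP 9.6.3 and 9.6.5:** replace the restriction to responders with all subjects in the All-treated Population, and report the Kaplan-Meier median and quartiles of 9.6.6. State the same population for the 24-month OS estimate.
- **SAP 9.6.4:** replace the restriction to responders with a next treatment by the All-treated Population, analysed by Kaplan-Meier with the censoring in protocol 5.5.4. Add the endpoint to 9.6.6.
- **SAP 9.6.2:** leave the responder set for DOR as it is.
- **PFS or OS by response, if wanted:** label it exploratory and use a landmark analysis, with a landmark time suited to each disease group's assessment schedule.

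The cost is a SAP wording change and the matching table shells. No new data are needed.

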9.6.4 Time to Next Treatment

Time-to-next treatment defined as the time from the first dose date of acalabrutinib or pembrolizumab to the start of the next treatment other than the study treatment. Descriptive statistics will be presented.

The summary of time to next treatment including the mean, minimum, maximum, median, Q1 and Q3 are provided for all the responders who have the next treatment for each disease group.

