# 4.4 TIME-TO-NEXT TREATMENT AND SURVIVAL

Subjects who discontinue study therapy will continue to be followed for assessment of time-to-next therapy unless they withdraw consent for further follow-up. After discontinuing study therapy, subjects will also be contacted approximately every 12 weeks until death, withdrawal of consent by subject, loss to follow-up, or study termination by the sponsor, whichever comes first.

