#### Time-to-Next Treatment

Time-to-next treatment defined as the time from the first dose date of acalabrutinib or pembrolizumab to the start of the next treatment other than the study treatment. Kaplan-Meier methods will be used to estimate the event-free curves and corresponding quartiles (including the median). Data from subjects who have not received subsequent therapy will be censored at the earliest of death or the last time that lack of administration of a new therapy was objectively documented.

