2.2 Secondary Objectives

- To evaluate the activity of acalabrutinib and pembrolizumab as measured by response rate, duration of response, progression-free survival, overall survival, and time to next treatment.

2.3 Exploratory Objectives:

CCI

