8 MISSING VALUES

No imputation of values for missing data will be performed except that missing or partial start and end dates for AEs and concomitant medication will be imputed according to prespecified, conservative imputation rules. Subjects lost to follow-up (or drop out) will be included in statistical analyses to the point of their last evaluation.

Imputation of partial dates will be made for AE onset and stop dates, start and end dates of concomitant medication, start date of subsequent anticancer therapy, date of initial diagnosis and death date. If dates are completely missing, no imputation will be made. For any partial date with missing year, no imputation will be made.

The general rule for imputation is:

- If only day is missing, then the 15th of the month will be used.
- If only year is present, then June 30th will be used.

If such imputation date for initial diagnosis is on or after date of first dose, the date of first dose – 1 will be used. If such imputed date for subsequent anticancer therapies is before date of last dose, the date of last dose + 1 will be used.

If the imputed date is for an AE start date and is in the same year and month as the first dose date but before the first dose date, then the first dose date will be used, or if the imputed AE start date is after the AE end date, then the AE end date will be used. If the imputed date is for an AE start date and is in the same year and month as but after the last dose date + 30 days, then the last dose date + 30 days will be used.

If the imputed date is for an AE end date and is after the death date, the date of death will be used, or if the imputed AE end date is before the AE start date, the AE start date will be used.

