10 CHANGES FROM PROTOCOL-SPECIFIED ANALYSES

There is no major change from protocol-specified analyses.

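### SAP 9.6.4 swaps the protocol's Kaplan-Meier analysis of time to next treatment for a summary of responders who went on to next treatment, and SAP 10 does not declare the change

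*SAP*

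**What the plan says.** Time to next treatment is one of five activity measures in the secondary objective; SAP 2.2 ends its list with "progression-free survival, overall survival, and time to next treatment".

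The Time-to-Next Treatment paragraph of Protocol 5.5.4 runs the clock from first dose to the start of the next non-study treatment. On method it says "Kaplan-Meier methods will be used to estimate the event-free curves and corresponding quartiles (including the median". On censoring it says "Data from subjects who have not received subsequent therapy will be censored at the earliest of death or the last time" that absence of new therapy was objectively documented. It does not limit the analysis to responders. Protocol 5.3 and SAP 6.1 put the primary efficacy analyses on the All-treated population.

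SAP 9.6.4 keeps the definition but calls for descriptive statistics. Its summary measures "are provided for all the responders who have the next treatment for each disease group". SAP 9.6.6 then says "The analysis of DOR, PFS, and OS will be estimated using the Kaplan-Meier (KM) method" and does not name time to next treatment. Appendices 12.2, 12.3 and 12.4 give censoring rules for duration of response, PFS and OS only. SAP 10 states "There is no major change from protocol-specified analyses".

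**The concern.** The SAP changes three things at once: the estimator, the treatment of censored subjects and the population. The resulting summary is selected on two outcomes that occur after first dose, namely responding and having the event. Subjects who go longest without new therapy drop out because they have not had the event, and non-responders drop out altogether.

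The two selections are likely to pull in opposite directions. Requiring the event removes the longest times and shortens the median. Restricting to responders probably lengthens it. A reader of the study report could not tell which way a cohort's figure is off, and SAP 10 would have told them that nothing of note had changed. Results are reported by histology, so each small cohort carries the problem separately.

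A related but smaller point concerns SAP 9.6.3 and 9.6.5, which ask for mean, median and quartiles of PFS and OS among responders. Both clocks start at first dose and response comes later. A responder must therefore have survived, progression-free, to the time of response, and these tables carry guarantee-time bias.

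**Working it through.** **1. The texts side by side**

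| Item | Protocol 5.5.4 | SAP |
|---|---|---|
| Estimator | Kaplan-Meier curve, median, quartiles | Descriptive statistics (9.6.4); not in the Kaplan-Meier list (9.6.6) |
| No next treatment yet | Kept and censored | Not in the summary; no censoring table in Section 12 |
| Non-responders | Included | Not in the summary |
| Change declared | n/a | None (SAP 10) |

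The data for the protocol analysis are collected. Protocol 4.4 says "Subjects who discontinue study therapy will continue to be followed for assessment of time-to-next therapy unless they withdraw consent for further follow-up", with no condition on response. SAP 8 already imputes a partial "start date of subsequent anticancer therapy".

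**2. Inputs for an illustration**

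The plan states no figure to reproduce: there are no rates for this endpoint and no data cutoff. The assumptions are:

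- Exponential times and a common follow-up F.
- Base case F = 32 months. Enrollment closed in May 2017 (Protocol 5.1) and the SAP is dated 17 January 2020, which is 31.6 to 32.6 months.
- Range 24 to 59 months. The upper end comes from the longest exposure, 30.2 months at 03 September 2017 (Protocol 1.4.2.1). That implies a first dose about 27 February 2015, 58.6 months before the SAP date.

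**3. How many subjects enter the summary**

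Take a 30-subject cohort at the 20% response rate of SAP 3.2: at most 0.20 × 30 = 6 can enter. If responders' true median is 24 months, the share with next treatment by month 32 is 1 − 2^(−32/24) = 0.603, so about 0.603 × 6 = 3.6 enter. At a 50% response rate the maximum is 15 and about 0.603 × 15 = 9.0 enter.

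**4. Effect of requiring the event**

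For true median m and median time to death d (infinite if no deaths), let r = ln2/m + ln2/d. The median among subjects with an observed event is

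t = −ln(1 − 0.5 × (1 − exp(−rF))) / r.

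For m = 24, no deaths, F = 32: r = 0.02888, exp(−rF) = 0.397, and t = −ln(0.6985)/0.02888 = 12.4 months.

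| True median (months) | F = 24 | F = 32 | F = 48 |
|---|---|---|---|
| 6 | 5.5 | 5.8 | 6.0 |
| 12 | 8.1 | 9.5 | 11.0 |
| 24 | 10.0 | 12.4 | 16.3 |
| 36 | 10.6 | 13.6 | 18.6 |

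At F = 59, true medians of 12 and 24 read as 11.4 and 18.2. With independent deaths at a median of 24 months and F = 32, they read as 7.3 and 9.5. For a true median of 36 and F = 32, Kaplan-Meier would report the median as not reached; the SAP summary would print 13.6.

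**5. Adding the responder restriction**

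Suppose responders have a median of 24 months and non-responders 6, with no deaths and F = 32. The SAP figure is 12.4 whatever the response rate. The all-treated median solves q·2^(−t/24) + (1 − q)·2^(−t/6) = 0.5, where q is the response rate:

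- q = 0.20 gives t = 7.4 months
- q = 0.50 gives t = 11.2 months

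If response makes no difference and everyone has a median of 24, the SAP figure is again 12.4. One reported value is thus compatible with all-treated medians of 7.4, 11.2 and 24 months.

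**6. PFS and OS**

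SAP 9.6.6 keeps Kaplan-Meier analyses of both on the All-treated population, so the bias is confined to the added responder tables. SAP 9.6.3 and 9.6.5 give censoring dates but do not say how censored times enter a mean, median or quartile in those tables.

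Two wording points arise in the same sections. SAP 9.6.3 censors subjects with no post-baseline assessment on Day 1, while Appendix 12.3 counts death before the first adequate assessment as an event; that row has effect only if the death takes precedence. SAP 9.6.3 and 9.6.5 also cite Appendices 14.4 and 14.5, where the tables are 12.3 and 12.4.

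**The case against.** The strongest reply is that the SAP never expressly withdraws Kaplan-Meier for this endpoint. Its stated purpose is to detail the protocol's analyses, the general sentence on descriptive statistics in 9.6.4 carries no population limit, and the protocol already gives the censoring rule in full without deferring it to the SAP. That is fair as a description of the text. But someone programming from the SAP would produce no curve and would find no censoring rule, and the only summary whose population is defined is the selected one.

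A second reply is that the numbers depend on the inputs chosen. The SAP date is not a data cutoff. The trial is defined to end 48 months after the last enrollment, about May 2021, and at 48 months the bias is smaller (11.0 and 16.3). The earliest subjects could then have about 75 months, at which the formula gives 11.8 and 20.2. When the true median is 6 months the event-only bias is slight. The scenarios in step 5 are chosen for illustration and are not a bias range. All of this stands, and it limits what can be said about size. It does not repair the summary.

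Third, this is a nonrandomized proof-of-concept study with a safety primary objective and no formal hypothesis test, and no stated decision rests on this endpoint. That bears on priority. Kaplan-Meier is itself descriptive here, and it is what the protocol chose.

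Two limits remain. Kaplan-Meier with deaths censored assumes that death is unrelated to the risk of next treatment, so the protocol analysis is not assumption-free. And the amendment number of the protocol copy used here could not be checked against the Amendment 6 named in SAP 1.

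**Conclusion.** The concern holds and should be fixed. As written, the SAP gives no valid estimate of time to next treatment for the treated cohort, and the departure from the protocol is undeclared. Calling it not major is hard to sustain when estimator, censoring and population all change for a named secondary endpoint.

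The size is illustrative. Over 24 to 59 months of follow-up without deaths, requiring the event turns a true 12 months into 8.1 to 11.4 and a true 24 months into 10.0 to 18.2. The responder restriction then moves the figure by an unknown amount, probably upward. These values assume exponential times and common follow-up; the conclusion that the summary is doubly selected does not. The PFS and OS responder tables are a lesser matter because their All-treated analyses remain planned.

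**What to change.** - **SAP 9.6.4:** remove the restriction to responders with next treatment. Specify the Protocol 5.5.4 analysis on the All-treated population: Kaplan-Meier curve, median and quartiles, with subjects without subsequent therapy censored at the earlier of death and the last objective documentation that no new therapy had started.
- **SAP 9.6.6 and Section 12:** add time to next treatment to the Kaplan-Meier list and give it a censoring table. Including it in the summary of censoring reasons would also show how many subjects are censored by death.
- **SAP 10:** if the change is intended, declare and justify it there instead.
- **SAP 9.6.3 and 9.6.5:** replace the responder summaries with the All-treated Kaplan-Meier medians and quartiles, and keep responder-only summaries for duration of response.
- **Wording:** state in 9.6.3 that the Appendix 12.3 row for death before the first adequate assessment (on or before subsequent therapy or data cutoff, whichever came first) overrides Day-1 censoring. Correct the references to 14.4 and 14.5 to 12.3 and 12.4.

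The cost is SAP wording, one censoring table and one Kaplan-Meier output by histology. No new data are needed. The reported PFS and OS summaries may look less favourable once the responder tables go.
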